8.4.4.2. Atrial fibrillation (AF)

AEs of AF are considered as AESI in this study.

In the efficacy study (RSV OA=ADJ-006), at the time of safety analysis (data lock point [DLP]) of 30 April 2022, a numerical imbalance in events of AF was observed within 30 days post-vaccination, with 10 events of AF (among which 7 [0.1%] were serious) in the RSVPreF3 group versus 4 (among which 1 [<0.1%] was serious) in the placebo group. No imbalance was observed for serious events of AF reported within 6 months post-vaccination. To further characterize events of AF, AF will be considered as an AESI.

When there is enough evidence to make the above diagnosis, the AE must be reported as AESI. Symptoms, signs or conditions which might (or might not) represent AF, should be recorded and reported as AEs but not as AESI until the final or definitive diagnosis has been determined, and alternative diagnoses have been eliminated or shown to be less likely.

For each case of AF reported in the AE or SAE section in the eCRF, additional information will be collected in a specific 'AF follow-up questionnaire' eCRF screen.

8.4.4.3. AESI for Transplant patients

Within the framework of the study, transplant rejection that occurs at any time during the study will be considered and recorded as an AESI.

Transplant rejection occurs when transplanted tissue is rejected by the recipient's immune system, which destroys the transplanted tissue. Diagnosis of rejection relies on patient signs and symptoms, laboratory data, imaging or other technical procedures and/or tissue biopsies. The investigator will take into consideration all available information, including biopsy results, to decide whether or not organ rejection occurs.

Clinically, management of allograft rejection will be as per local standard of care.

Any form of rejection should be recorded and reported to the sponsor or designee as indicated in Section [10.3](#).

When there is enough evidence to make any of the above diagnoses, the AE must be reported as AESI. Symptoms, signs or conditions which might (or might not) lead to one of the above diagnoses, should be recorded and reported as AEs but not as AESIs until the final or definitive diagnosis has been made, and alternative diagnoses eliminated or shown to be less likely.

8.4.5. Regulatory reporting requirements for SAEs/pregnancies/AESIs

Prompt notification by the investigator to the sponsor of an SAE/pregnancy/AESI is essential so that legal obligations and ethical responsibilities toward the safety of participants and the safety of a study intervention under clinical investigation are met. See Section [8.4.1](#) for reporting timeframes.

For SAEs/AESIs, the investigator must always provide an assessment of causality at the time of the initial report, as defined in Section [10.3.5.6](#).

An investigator who receives an investigator safety report describing an SAE or other specific safety information (e.g., summary or listing of SAEs) from the sponsor will review and then file it along with the IB and will notify the IRB/IEC, if appropriate according to local requirements.

Table 18 Timeframes for submitting SAEs, pregnancies and AESIs to GSK

Type of event	Initial reports		Follow-up of relevant information on a previous report	
	Timeframe	Documents	Timeframe	Documents
SAEs	24 hours*	electronic AEs Report	24 hours*	electronic AEs Report
Pregnancies	24 hours*	electronic pregnancy report	24 hours*	electronic pregnancy report
AESIs	24 hours**	electronic AEs Report	24 hours*	electronic AEs Report
Serious AF***	24 hours**	electronic AEs Report + AF follow-up questionnaire	24 hours*	electronic AEs Report + AF follow-up questionnaire

* Timeframe allowed after receipt or awareness of the information by the investigator/site staff.

** Timeframe allowed once the investigator determines that the event meets the protocol definition of an AESI.

*** Only AF meeting SAE definition will be reported in electronic AEs Report and in the specific AF follow-up questionnaire. Non-serious AF will be reported in the non-serious adverse event eCRF screen and in the AF follow-up questionnaire.

8.4.6. Pregnancy

Female participants who become pregnant after the first study intervention dose must not receive subsequent doses of the study intervention but may continue other study procedures at the discretion of the investigator.

Female participants who become pregnant after administration of the study intervention may continue other study procedures at the discretion of the investigator.

Details of all pregnancies in female participants will be collected after the start of study intervention and until end of study (refer Section 5.1 for details).

If a pregnancy is reported, the investigator will record pregnancy information on the appropriate form and submit it to the sponsor within 24 hours of learning of the female participant's pregnancy.

Any pregnancy complication or elective termination of a pregnancy for medical reasons will be reported as an AE or SAE.

Abnormal pregnancy outcomes (e.g., spontaneous abortion, fetal death, stillbirth, congenital anomalies, ectopic pregnancy) are considered SAEs and will be reported as such. The participant will be followed to determine the outcome of the pregnancy. The investigator will collect follow-up information on the participant and the neonate and the information will be forwarded to the sponsor. See Table 18 for reporting timeframes.

Any post-study pregnancy-related SAE considered reasonably related to the study intervention by the investigator will be reported to the sponsor as described in Section 8.4.4. While the investigator is not obligated to actively seek this information in former study participants, he or she may learn of an SAE through spontaneous reporting.

Any female participant who becomes pregnant while participating in the study will discontinue study intervention.

8.4.8. Participant card

The investigator (or designee) must provide the participant/participant's parent(s)/LAR(s) with a "participant card" containing information about the clinical study. The participant/participant's parent(s)/LAR(s) must be instructed to always keep the participant card in their possession for the duration of the study. In an emergency, this card serves to inform the responsible attending physician/LAR/caregiver that the participant is in a clinical study and that relevant information may be obtained by contacting the investigator(s) or their back up.

8.5. Pharmacokinetics

PK is not evaluated in this study.

8.6. Pharmacodynamics

PD is not evaluated in this study.

8.7. Genetics

Genetics are not evaluated in this study.

8.8. Biomarkers

Biomarkers are not evaluated in this study.

8.9. Immunogenicity assessments

Immunogenicity is described in Section 8.2

8.10. Health economics or medical resource utilization and health economics

Not applicable for this study.

9. STATISTICAL CONSIDERATIONS

9.1. Statistical Hypotheses

The primary objective, as outlined in Section 3, will be addressed using an estimation approach with no hypothesis testing. For the primary estimand, descriptive analysis will be utilized.

9.2. Analysis sets

Analysis sets are presented in [Table 20](#).

Table 20 Analysis sets

Analysis Set	Definition / Criteria	Analyses Evaluated
Screened Set	All participants who were screened for eligibility.	Study Population
Enrolled Set	All participants who entered the study (who were randomized or received study intervention administration or underwent a post-screening study procedure). NOTE: screening failures (who never passed screening even if rescreened) and participants screened (met eligibility) but never enrolled into the study are excluded from the Enrolled Set as they did not enter the study.	Study Population
Exposed Set (ES)	All participants who received the study intervention administration. Analysis per group is based on medical condition (IC versus healthy adults) and according to the randomization (RSV_IC_1 versus RSV_IC_2 group)..	Study Population, Safety
Per Protocol Set* (PPS)	All eligible participants 
 • who received the study intervention administration as per protocol • had immunogenicity results pre- and post-dose • complied with blood draw intervals • without intercurrent conditions that may interfere with immunogenicity • without prohibited concomitant medication/vaccination. Analysis per group is based on medical condition (IC versus healthy adults) and according to the randomization (RSV_IC_1 versus RSV_IC_2 group).	Immunogenicity

* Contribution of participants to PPS will be defined by timepoint.

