4. STUDY DESIGN

4.1. Overall design

The study design overview is presented in [Figure 1](#).

Experimental design: Phase 2b, randomized, multi-center, open-label study with three parallel groups (see [Figure 1](#)).

Study groups and Randomization and enrollment rules: Approximately 375 eligible participants will be enrolled in the study, under the following groups.

- Approximately 250 IC adults ≥ 18 YoA who received a renal or lung SOT, will be randomly assigned (1:1) to the following 2 IC groups (1 dose versus 2 doses; 125 participants each) at Visit 1 (Day 1). Each group may include approximately 65% renal transplant patients and approximately 20% lung transplant patients, and the remaining patients can be freely distributed across the 2 groups.
 - **RSV_IC_1 group:** IC patients receiving 1 dose of RSVPreF3 OA investigational vaccine at Visit 1 (Day 1).
 - **RSV_IC_2 group:** IC patients receiving 2 doses of RSVPreF3 OA investigational vaccine at Visit 1 (Day 1) and Visit 3 (Visit 1 + 30-60 days).
- Approximately 125 healthy adults ≥ 50 YoA (distributed among age categories of 50-59 YoA (30 %), 60-69 YoA (30%), ≥ 70 YoA (20%), and 20% to be freely distributed over the different age categories) will be assigned to the healthy participants group.
 - **RSV_HA group:** Healthy participants receiving 1 dose of RSVPreF3 OA investigational vaccine at Visit 1 (Day 1).

Primary completion date: Visit 4 (1 month after the last study intervention administration).

Duration of the study: The total duration of the study, per participant, will be approximately 13-15 months for the IC patients and 12 months for the healthy participants.

Type of study: self-contained.

Data collection: A standardized eCRF will be used. Solicited events will be collected as of the day of each study intervention administration and for 6 subsequent days. Unsolicited AEs, new concomitant medications/vaccinations will be collected as of the day of each study intervention administration and for 29 subsequent days. As of Day 30 following each study intervention administration, the details are collected in source documents prior to entering them in the eCRF until study end.

Safety monitoring: The study will be monitored by an IDMC as well as the project SRT (Refer Section 8.3.4 and Section 10.1.6).

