7. DISCONTINUATION OF STUDY INTERVENTION AND PARTICIPANT DISCONTINUATION/WITHDRAWAL

7.1. Discontinuation of study intervention

Discontinuation of study intervention refers to any participant who has not received all planned doses of the study intervention. In rare instances, it may be necessary for a participant to permanently discontinue study intervention. If study intervention is permanently discontinued, the participant should, if possible, continue other study procedures (e.g., safety or immunogenicity), planned in the study protocol at the discretion of the investigator.

The primary reason for premature discontinuation of the study intervention will be documented in the eCRF based on the list below:

Reasons	Additional items/Sub-reasons
AE	Unsolicited AE
	Solicited AE
	SAEs / pIMDs /AESIs
Lost to follow-up	
Withdrawal by Participant	Burden of Procedure
	Participant Relocated
	COVID-19

Reasons	Additional items/Sub-reasons
	Other, Specify
Investigator Decision	Specify
Protocol Deviation	Specify
Site Terminated by Sponsor	
Study Terminated by Sponsor	
Pregnancy	
Death	
Other	Specify

AE = Adverse event; AESI = Adverse event of special interest; COVID-19 = Coronavirus disease; pIMD = Potential immune-mediated disease; SAE = Serious adverse event.

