7.1.1. Contraindications to subsequent study intervention administration

The eligibility for subsequent study intervention administration must be confirmed before administering any additional dose.

Participants who meet any of the criteria listed below or criteria listed in Sections [5.2.1](#) and [5.2.2](#) should not receive additional doses of study intervention. Such participants should be encouraged to continue other study procedures, at the investigator's discretion. All relevant criteria for discontinuation of study intervention administration must be recorded in the eCRF.

- Participants who experience any SAE judged to be possibly or probably related to study intervention or non-study concomitant vaccine/product, including hypersensitivity reactions.
- Participants who develop any new condition which, in the opinion of the investigator, may pose additional risk to the participants if they continue to participate in the study.
- Anaphylaxis following the administration of study intervention.
- Condition that in the judgment of the investigator would make intramuscular injection unsafe.
- Occurrence of a new pIMD or the exacerbation of an existing pIMD that, in the opinion of the investigator, expose the participant to unacceptable risk from subsequent vaccination. In such cases, the investigator should use their clinical judgment prior to administering the next dose of the study intervention. Refer to Section [8.4.4.1](#) for the definition of pIMD.
- Occurrence of a new AESI or the exacerbation of an existing AESI that, in the opinion of the investigator, exposes the participant to unacceptable risk from subsequent doses of study intervention. Refer to Section [8.4.4](#) for the definition of AESI.

- Pregnant or lactating female participant (Refer to Section 8.4.6).

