9.3.2. Secondary endpoints/estimands analyses

Refer to Section 3 for the definition of secondary immunogenicity (humoral and CMI response) and safety endpoints. The immunogenicity analysis will be based on the PPS and safety analysis will be based on the ES.

For humoral immune response, the following analysis will be tabulated for each immunological assay (RSV-A and RSV-B neutralization titers):

- Percentage of participants above predefined threshold and GMT, with 95% CI, at pre-study intervention administration (Visit 1), Visit 2 (in a subset of participants), Visit 3, Visit 4, Visit 5, and Visit 6 in all groups.
- GMT ratio (RSV_HA group over RSV_IC group (pooled RSV_IC_1 and RSV_IC_2 group) with 95%CI, at Visit 2 (in a subset of participants) and Visit 3.
- GMT ratio (RSV_IC_2 group over RSV_IC_1 group) with 95% CI, at Visit 4, Visit 5, and Visit 6.
- GMT ratio (RSV_HA group over RSV_IC_1 group) with 95% CI, at Visit 4, Visit 5, and Visit 6.
- GMT ratio (RSV_HA group over RSV_IC_2 group) with 95%CI, at Visit 4, Visit 5, and Visit 6.
- MGI (RSV_IC group [pooled RSV_IC_1 and RSV_IC_2 group] and RSV_HA group) with 95% CI, at Visit 2 (in a subset of participants) over Visit 1, and at Visit 3 over Visit 1.

- MGI (RSV_IC_1, RSV_IC_2 and RSV_HA group) with 95% CI, at Visit 4, Visit 5 and Visit 6 over Visit 1.

The GMT ratios and their 95% CIs will be derived from an ANCOVA model on log10-transformed titers (details will be provided in the SAP).

The following analysis will be tabulated by group for CMI response in the CMI subset:

- Descriptive statistics (N, geometric mean, min, Q1, median, Q3, max) for the frequency of RSVPreF3-specific CD4+ and/or CD8+ T cells expressing at least 2 activation markers including at least one cytokine among CD40L, 4-1BB, IL-2, TNF- α , IFN- γ , IL-13, IL-17 at pre-study intervention administration (Visit 1), Visit 2, Visit 3, Visit 4, Visit 5, and Visit 6 in all groups.

Descriptive safety analysis by group will be summarized as follows:

- Percentage of participants reporting each solicited administration site event and solicited systemic event during a 7-day follow-up period (i.e., on the day of study intervention administration and 6 subsequent days) after each study intervention administration.

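### The randomised 2-dose/1-dose titre ratios at Visits 4 to 6 rest on the per-protocol set alone, and its dosing criterion for dose 2 can exclude participants from one arm only

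*Protocol*

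**What the plan says.** Section 9.3.2 fixes the analysis set: "The immunogenicity analysis will be based on the PPS and safety analysis will be based on the ES". Table 20 agrees. It lists immunogenicity against the PPS only and gives the Exposed Set to study population and safety.

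Among other criteria, the PPS requires eligible participants "who received the study intervention administration as per protocol". The table's footnote adds: "Contribution of participants to PPS will be defined by timepoint".

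The contrast at issue is listed in Section 9.3.2 as "GMT ratio (RSV_IC_2 group over RSV_IC_1 group) with 95% CI, at Visit 4, Visit 5, and Visit 6", from an ANCOVA on log10 titres. Section 4.2 explains that the 1-dose transplant group is there to inform the choice between one and two doses through GMT ratios and cell-mediated immunity.

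Section 4.1 gives RSV_IC_1 one dose at Visit 1, and RSV_IC_2 a further dose at Visit 3. Section 7.1.1 says of that further dose: "The eligibility for subsequent study intervention administration must be confirmed before administering any additional dose". Of someone who stops the intervention, Section 7.1 says "the participant should, if possible, continue other study procedures", and it names immunogenicity among those procedures.

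**The concern.** The two IC arms are randomised 1:1 and receive the same first dose, so a difference from Visit 4 on should reflect the second dose. That holds only while membership of the analysed group does not depend on what happens after randomisation in one arm.

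Here it does depend on it in part. Being dosed as planned is settled at Visit 1 for RSV_IC_1, but only at Visit 3 for RSV_IC_2. Between those visits a participant can fall ill, meet a contraindication, miss the visit or, in an open-label trial, decline the second injection. A counterpart in RSV_IC_1 has no second injection to miss and can stay in the analysis. If the people lost from RSV_IC_2 differ in antibody response from the rest, the ratio mixes the effect of the dose with that selection.

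At stake is the only randomised comparison of one dose with two. The primary endpoint, the MGI of Visit 4 over Visit 3, is a within-arm measure in RSV_IC_2.

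**Working it through.** **1. The plan's own figures.** Section 9.5.1 assumes 100 evaluable per group, log10-titre SDs of 0.45 (healthy) and 0.50 (IC), and one-sided 2.5%. I used a noncentral t with ncp = log10(fold) / √(s₁²/n₁ + s₂²/n₂) and Satterthwaite degrees of freedom. At 80% power:

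- healthy vs one IC group (100 vs 100): 1.547; the plan states 1.55
- healthy vs pooled IC (100 vs 200): 1.449; the plan states 1.45
- attrition: 100 / (1 − 0.20) = 125 per group, as stated

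The plan's figures reproduce. It gives none for RSV_IC_2 vs RSV_IC_1. With SD 0.50 in both arms and 100 per arm, the detectable fold difference is 1.58. SE = √(2 × 0.25/100) = 0.0707, so the 95% CI half-width is 10^(1.972 × 0.0707) ≈ 1.38-fold.

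**2. Who leaves each arm, by route.**

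| Event after Visit 1 | RSV_IC_2 at Visits 4–6 | RSV_IC_1 at Visits 4–6 |
|---|---|---|
| Refuses dose 2, or misses it | fails the dosing criterion | no dose due, criterion met |
| Dose 2 given off-window | fails the dosing criterion | no dose due; a late Visit 3 bears only on blood-draw intervals |
| Meets a 7.1.1, 5.2.1 or 5.2.2 criterion | dose 2 withheld, fails the dosing criterion | may be eliminated under 9.2.1 |
| Intercurrent condition affecting immunity | may be eliminated | may be eliminated |

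The schedules of activities match this: contraindications are rechecked at Visit 3 in Table 2 (RSV_IC_2), but checked only at Visit 1 in Table 1 (RSV_IC_1). The Visit 3 blood sample precedes dose 2, so Visit 3 results are unaffected.

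**3. Size, as an illustration.** Let f be the share of RSV_IC_2 without dose 2, and d the amount by which such people's one-dose log10 titres fall below the rest. Suppose their counterparts all stay in RSV_IC_1. If the remaining participants have mean m under one dose, the RSV_IC_1 mean is (1 − f)m + f(m − d) = m − fd, while the filtered RSV_IC_2 arm averages m plus any dose effect. The ratio is multiplied by 10^(f·d). Neither f nor d is in the protocol, so both are assumed:

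- f = 5%, d = 0.2: 10^0.010 = 1.02
- f = 10%, d = 0.3: 10^0.030 = 1.07
- f = 15%, d = 0.5: 10^0.075 = 1.19
- middle case, with half the counterparts also removed from RSV_IC_1 under 9.2.1: 10^0.015 ≈ 1.04
- middle case with the sign reversed (d = −0.3): 10^−0.030 = 0.93

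In the middle case, with no true effect of dose 2, the chance that the lower 95% limit exceeds 1 is P(Z > 1.96 − 0.030/0.0707) ≈ 6%, against 2.5%.

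**4. What an as-randomised analysis gives.** The same algebra gives (1 − f) times the log effect in those who get dose 2, with no term in d. At f = 10%, a 1.58-fold effect would read as 1.58^0.9 ≈ 1.51.

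**The case against.** The strongest reply is Section 9.2.1. It says that participants who meet the 7.1.1, 5.2.1 or 5.2.2 criteria, or who incur an intercurrent condition, may be eliminated from the per-protocol analysis, and it does not confine this to RSV_IC_2. SAEs, pIMDs, transplant AESIs and intercurrent conditions are recorded in both IC arms at every visit from Visit 1, so the rule could be applied evenly. A reader might infer that health-related exclusions fall on RSV_IC_2 alone; the protocol does not support that. What survives is that 9.2.1 is discretionary while the dosing criterion in Table 20 is not, and that refusal, a missed dose or an off-window dose has no dosing counterpart in RSV_IC_1.

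Second, Section 9.3 leaves supportive analyses to the SAP, which is not at hand and may contain an Exposed Set run. That is fair, and it means nobody can say such an analysis is absent from the plan as a whole. But the protocol does fix the set for this contrast, and that choice can be judged as it stands.

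Third, a reader might infer that the excluded participants are weaker responders, so that the PPS inflates the benefit of dose 2. The documents do not show this. The 7.1.1 list includes anaphylaxis, hypersensitivity, a new pIMD and pregnancy, none of which implies a low titre.

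Fourth, the stakes are limited. The contrast is secondary, the study is descriptive without hypothesis tests, and Section 4.2 presents the comparison as an aid to the dosing decision, not as its rule. All of that stands.

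**Conclusion.** The structural point holds. The PPS is the only set the protocol names for these ratios, its dosing criterion applies by timepoint, and one randomised arm alone has a second dose to miss. The Visit 4 to 6 contrast is therefore not fully protected by randomisation. To say that it has lost its randomisation would go too far: groups are still analysed as allocated, and part of the exclusion can be even-handed.

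The direction and size of any bias are unknown. Section 7.1 expects permanent discontinuation to be rare, and the 20% attrition allowance covers all reasons in all groups, so it says nothing about missed second doses. The factor of 1.07 depends on three assumptions: 10% without dose 2, titres 0.3 log10 lower, and no matching exclusion in RSV_IC_1. It is small beside a CI half-width of about 1.38-fold. The 1.19 case needs 15% and a deficit of one full planning SD (0.50). This is an inexpensive improvement to a secondary analysis and does not touch the primary endpoint.

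**What to change.** In Table 20, add immunogenicity to the Exposed Set for this contrast. In Section 9.3.2, state that the RSV_IC_2 over RSV_IC_1 GMT ratios at Visits 4, 5 and 6 will also be estimated, with the same ANCOVA, in all exposed IC participants who have a titre at that visit, in their randomised group and whether or not dose 2 was given. Report them beside the PPS ratios.

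No new set, visit or sample is needed. The Exposed Set already groups IC participants by randomisation, and entry to it depends on the first dose, which is the same in both arms. Participants who stop the intervention are already asked to stay for immunogenicity procedures where possible.

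The cost is one more analysis run and slight dilution towards no difference from those without dose 2. The result still depends on a titre being available, so the number of RSV_IC_2 participants without dose 2, and how many of them have a titre at each visit, should be shown with it.
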